APPENDIX 7: Study outcome definition and measurement

Research question	Question and outcome type	Outcome measure	Presented as	Method of outcome data collection
2.6 Do active drops reduce overall symptom burden (including episodes of crying/ distress, disturbed sleep, interference with normal activity, appetite and fever) in the first 7 days after randomisation compared to placebo drops and no drops (usual care)?	Secondary	Numeric: Total number of symptoms and average severity of symptoms over the first 7 days after randomisation	Mean/Median/Log mean severity of other symptoms in the first 7 days after randomisation (depending on the distribution).	Daily Symptom and Recovery Questionnaire (Days 1-8) with telephone support calls during week 1
2.7 Do active drops alter overall illness duration (defined as the last day post randomisation on which parent-reported child ear pain scores zero for two consecutive days without other analgesic medication) compared to placebo drops and no drops (usual care)?	Secondary	Numeric: number of days post randomisation on which the parent reports a score >0 for the child's ear pain or gives the child analgesics for ear pain	Number of days until child's ear pain resolves for two consective days pain free without medication (this will give us a start date but not necessarily an end date for antibiotic consumption).	Daily Symptom and Recovery Questionnaire (Days 1-8) with telephone support calls during week 1
2.8 What are the net incremental costs to the NHS (e.g. fewer antibiotic prescriptions) and society (e.g. parental productivity) of using active ear drops compared to no drops (usual care) in the short (7 days after randomisation) and medium term (3 months)?	Secondary	To be defined in the Economic Analysis Plan	To be defined in the Economic Analysis Plan	Symptom and Recovery Questionnaire (Day 8) with telephone support call, and review of primary care medical notes at 3 months
2.9 To conduct an economic analysis to explore whether the net incremental costs of active ear drops are justified by improved pain relief, symptom burden, antibiotic use or quality of life.	Secondary	To be defined in the Economic Analysis Plan	To be defined in the Economic Analysis Plan	Symptom and Recovery Questionnaire (Day 8) with telephone support call, review of primary care medical notes at 3 months, and QoL postal questionnaire at 3 months
2.10 To use qualitative methods to investigate parents' and clinicians' views	Secondary			Qualitative interviews

APPENDIX 7: Study outcome definition and measurement

Researc	h question	Question and outcome type	Outcome measure	Presented as	Method of outcome data collection
and experiences of AOM in children in the CEDAR trial, and specifically to:					
2.10.1	To explore through qualitative methods parents' views, beliefs and expectations about AOM and its treatment.	Secondary	N/A	Inductive thematic analysis using constant comparison techniques.	Qualitative interviews with parents
2.10.2	To understand parents' and clinicians' experiences of the trial, including their experiences and opinions of treatments for AOM, including barriers, facilitators and adherence to treatments.	Secondary	N/A	Inductive thematic analysis using constant comparison techniques.	Qualitative interviews with parents and clinicians
2.10.3	To examine reasons for parents' declining trial participation or withdrawing from the trial	Secondary	N/A	Inductive thematic analysis using constant comparison techniques.	Qualitative interviews with parents who decline trial participation
2.10.4	In preparation for disseminating the trial results, to explore the information and support needs of parents and clinicians in relation to AOM and its treatment.	Secondary	N/A	Inductive thematic analysis using constant comparison techniques.	Qualitative interviews with parents and clinicians
of t pre	To investigate the representativeness he CEDAR trial sample by describing the sentation, management and outcome hildren with AOM in primary care.	Secondary	To be defined after data collection and analysis	To be defined after data collection and analysis	Database Search, Screening Log and Case Report Form (for RCT and observational cohort study)

Auralgan Ear Drops

PRODUCT INFORMATION

Product description

Auralgan Ear Drops is a clear colourless to light amber viscous liquid. Refer to presentation for a complete description of the dosage form. Each 1mL of ear drops solution contains:

Phenazone, 54mg Benzocaine 14mg

This product also contains hydroxyquinoline sulfate and glycerol.

Pharmacology

Pharmacokinetics:

Phenazone is absorbed from the gastro-intestinal tract and distributed throughout the body fluids. Less than 10% is bound to plasma proteins and it has a half-life of about 12 hours. Phenazone is metabolised in the liver to 3 major metabolites 3-hydroxymethyl-phenazone, 4-hydroxyphenazone, and norphenazone. Phenazone, 3-hydroxymethylphenazone, and glucuronidated metabolites are all excreted in the urine. A small proportion may be eliminated via the bile.

Benzocaine, like most local anaesthetics, is readily absorbed through mucous membranes, and through damaged skin. Local anaesthetics are weak bases and at tissue pH can diffuse through connective tissue and cellular membranes to reach the nerve fibre where ionisation can occur. Anesthetics of the ester-type are hydolzed by esterases in the plasma and to a lesser extent in the liver. Most ester-type anesthetics have little protein binding.

Pharmacodynamics/Mechanism of action:

Phenazone is a non-steroidal anti-inflammatory drug (NSAID). The mechanism of action for otic use has not been established.

Benzocaine is an ester type local anesthetic. It is an ethyl ester of paraaminobenzoic acid (PABA) and has been used widely as a topical anesthetic. It shares the pharmacologic effects of other local anesthetics, and acts by blocking nerve conduction first in the autonomic, then in sensory and finally motor nerve fibers. Nerve conduction appears to be blocked by benzocaine as a result of a decrease in the permeability of the nerve cell membrane to sodium ions. Competition with calcium ions for membrane binding sites also appears to be involved. Local anesthetics may also reduce the permeability of resting nerves to potassium, as well as to sodium ions.

PI- Auralgan_2015-05-07A

APPENDIX 8: Auralgan Product Information (PI-Auralgan_2015-05-07A)

Due to its low aqueous solubility, benzocaine is poorly absorbed and systemic toxicity is rare however, methemoglobinemia has been observed following topical application.

Indications

Auralgan ear Drops is for the effective relief of ear pain associated with otitis media.

Contraindications

Auralgan Ear Drops is contraindicated for use:

- in patients with perforated ear drums
- if discharge from the ear is present
- in patients with known hypersensitivity to any of the ingredients in the product or to similar substances

Precautions

Auralgan Ear Drops should be used with caution in patients with the following ear problems:

- Pain lasting more than 24 hours
- Fever, dizziness, stiff neck, ear discharge
- Hearing loss or ringing in the ears
- Inability to walk properly
- In patients who have had a discharge from ears, a recent ear infection or had a burst ear drum in the past.

Carcinogenesis, mutagenesis, impairment of fertility: Long-term animal studies have not been performed to evaluate the carcinogenic or mutagenic potential of Auralgan Ear Drops. The effect of Auralgan Ear Drops on human fertility is not known.

Auralgan Ear Drops should be used with caution in patients with porphyria as phenazone is possible porphyrogenic.

This product should be kept out of reach of children.

Due to a potential increased risk of methemoglobinemia, use with caution in the following patients:

- Patients taking drugs such as sulphonamides or antimalarials as these may predispose to methemoglobinemia.
- Infants under 1 year of age.
- Patients with hemoglobinopathies or Glucose-6-phosphate dehydrogenase deficiency (G6PD).

Stop use and seek immediate medical attention if you have difficulty breathing; pale, gray or blue colored skin; weakness, confusion, or headache. These may be signs of a rare, but serious condition and may appear within minutes to hours after benzocaine use.

PI- Auralgan_2015-05-07A

Use in pregnancy

The safe use of Auralgan Ear Drops during pregnancy has not been established.

Lactation

Available evidence and/or expert consensus is inconclusive or is inadequate for determining infant risk when used during breastfeeding. Therefore it is not recommended for breastfeeding mothers unless the potential benefits to the patient are weighed against the possible risk to the infant.

Interaction with other medicines

- Hyaluronidase effectively increases the diffusion of local anesthetics. The beneficial effects of hyaluronidase are offset by an increased incidence of systemic toxic reactions due to increased absorption of the local anesthetic
- St John's Wort may increase the risk of cardiovascular collapse and/or delayed emergence from anesthesia

Adverse reactions

Due to its low aqueous solubility, benzocaine is poorly absorbed and systemic toxicity is rare however, methemoglobinemia has been observed following topical application.

Benzocaine may cause the following symptoms: nausea and vomiting, whereas, Phenazone has been associated with the haemolytic anemia and agranulocytosis. Such reactions are unlikely following application of Auralgan on the external ear canal.

Hypersensitivity reaction consisting of rash, urticaria, oedema, anaphylaxis have been observed rarely with Benzocaine.

Symptoms such as vertigo, nausea, and nystagmus has been observed after local anaesthetic use in the external or middle ear and may be due to penetration of the local anaesthetic into the inner ear.

Individuals frequently exposed to ester-type local anaesthetics can develop contact dermatitis characterised by erythema and pruritis which may progress to vesiculation and oozing. Discontinue promptly if sensitisation or irritation occurs.

Dosage and Administration

- Use Auralgan Ear Drops at room temperature.
- If bottle is cold to the touch, warm in hand for a minute.
- Tilt head to one side with affected ear uppermost.
- Fill ear canal and plug ear with cotton wool moistened with Auralgan Ear Drops.
- Repeat every 1 to 2 hours until pain is relieved.

PI- Auralgan_2015-05-07A

APPENDIX 8: Auralgan Product Information (PI-Auralgan_2015-05-07A)

- If conditions persist, a doctor should be consulted.
- Avoid touching the ear with the dropper.
- Do not rinse dropper after use.
- Replace dropper in the bottle after use and cap tightly.

Overdosage

In case of accidental ingestion, contact the Poison Information Centre (Australia [name]; New Zealand [name]) immediately.

Presentation

Auralgan Ear Drops is a clear colourless to light amber viscous liquid, packed in bottle.

Marketed pack size: 15mL

Storage

Store below 25°C

Poison Schedule

Auralgan Ear Drops: Pharmacy Medicine

Name and address of the Sponsor:

Pfizer Australia Pty Limited [name] Australia 🖀 Toll Free [name]

Pfizer New Zealand Ltd Auckland, New Zealand New Zealand 🖀 Toll Free [name]

Date of TGA Approval : 16 April 2014

Date of Last Amendment: 3 July 2015

PI- Auralgan_2015-05-07A

APPENDIX 9: Randomisation, concealment and code-break

Each child for whom formal consent has been given by the parent or legal guardian will be randomised to one of the three arms of the trial: active ear drops plus usual care, placebo ear drops plus usual care, and usual care alone.

The randomisation schedule will be written by BRTC and will be stratified by Centre (Bristol, Cardiff, Southampton), with trial medicines (identified by a Medicine ID number) centrally randomised to patient packs (identified by a Participant ID number). The Centres will be provided with identical, sealed, sequentially numbered Patient Packs and with identical, sealed, numbered Medicine Packs (each containing a bottle of the active or placebo ear drops) to distribute to participating primary care sites. The centres will receive Patient Packs and Medicine Packs in a proportion of 3:2, in line with the ratio of treatment arms (usual care plus active drops or placebo drops) to the control arm (usual care and no drops). The sites will also receive Patient Packs and Medicine Packs in a proportion of 3:2.

Recruiting primary care sites will be given a set number of identical, sealed Patient Packs which will be distinguished by the unique Participant ID numbers. They will also be provided with a set of Medicine Packs which will be identified by the unique Medicine ID numbers. The patient packs will each contain a prerandomised Medicine ID number. The format of the Medicine ID number will specify whether the participant will be allocated to a treatment group (either the active ear drops or placebo ear drops, but the specific group will be concealed) or to the control arm. For participants in the treatment arms the Medicine ID number in the Patient Pack will match the Medicine ID number on one of the Medicine Packs with which the site has been provided. For participants in the control arm, there will be no Medicine Pack with a matching Medicine ID number.

Once participant eligibility is confirmed and written informed consent obtained, the parent will be given the next available sequentially numbered Patient Pack. If the Medicine ID number indicates that the child has been allocated to one of the medicine arms, the clinician will retrieve the single bottle of ear drops for which the Medicine ID number corresponds to that provided in the Patient Pack. For participants in the treatment arms, Quality Assurance will be achieved by asking a third party (another member of the practice team) to verify that the Medicine ID number in the Patient Pack has been correctly matched to the Medicine ID number on the Medicine Pack containing the bottle. For participants in the control arm, no matching will be necessary.

The patient ID number will be different to the Medicine ID number to enable flexibility in the numbers recruited at each Centre, allowing medicine packs to be combined with patient packs allowing for temporary fluctuations in recruitment rates between Centres.

The primary research question ("do drops reduce antibiotic consumption") is best addressed using a pragmatic, open design since knowledge of treatment allocation (as well as the treatment itself) is known to be an important driver of antibiotic consumption [[name] BMJ 2001] and will provide estimates of 'real world' pragmatic effect sizes. However, to investigate effects on pain (subjective outcome and secondary research question) requires a blinded design. One of the reasons to have a 1:1:1 randomisation strategy in the three arms is that the trial statistician will be blind to patient allocation.

The UH Bristol Pharmacy will hold the randomisation schedule and a log of which Medicine Pack was put into which Patient Pack (hereafter referred to as the Code-break) and provide a 24 hour emergency unblinding service. During working hours (Monday to Friday, 9am to 5pm), concerned clinicians should contact the UH Bristol Pharmacy Clinical Trials Unit on [name]. Out-of-hours, the Trust on-call Emergency Duty Pharmacist is available via the Trust switchboard [name]. Each parent will be given a Trial Participation Card with details of who the child's Responsible Clinician should contact in the event of an emergency. The Trial Manager and Centre Co-ordinators will also hold these cards.

A standardised procedure for breaking the code will be available (UH Bristol CT 5 01 Emergency Code Breaking). When necessary, the code for a particular participant can be broken at any moment during the trial. The codes will only be broken in case of a medical emergency, if unblinding will influence the child's treatment, or the child

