7.2. Packaging, labelling and dispensing

The supplier will be responsible for packaging the active and placebo medicines into identical containers and for labelling them under their MIA (IMP) license. The labelling of medication packs will be MHRA-approved and conform to Annexe 13 (GMP) and Article 13.3 of Directive 2001/20/EC. A template label will be provided by the supplier and approved by UH Bristol Pharmacy on behalf of the Sponsor in line with the Service Level Agreement (SLA), and by the Chief Investigator.

Each Medication Pack will have a Medicine ID number, randomly generated to ensure active and placebo ear drop solution bottles are indistinguishable (e.g. avoid all placebo bottles being assigned an odd number) and thus maintain allocation concealment. This random number will be generated by the Bristol Randomised Trials Collaboration and provided to the supplier who will use it to form the medicine identifier (Medicine ID Number) and include it with the open code break document sent with each delivery of trial Medicine Packs to UH Bristol Pharmacy. Each Medicine Pack will contain two bottles of either the active or the placebo solution.

The Medicine Packs will be received from the supplier and stored by the Pharmacy at University Hospitals Bristol NHS Foundation Trust (UH Bristol Pharmacy). A randomisation schedule will be provided to the supplier and to UH Bristol Pharmacy by the Bristol Randomised Trials Collaboration (BRTC) assigning active vs. placebo treatment to each Participant ID number (an interim 2-arm randomisation schedule will be applied for the 2 arm pilot at the start of the trial). The Participant ID number will have two digits will be configured to identify whether the child has been recruited into the RCT or OCS, the trial Centre in which they were recruited, followed by a sequence of digits.

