All RCT Patient Packs will be pre-labelled with the Participant ID number and will contain: (i) either a medicine pack (containing either 2 bottles of active solution, or 2 bottles of placebo) or an ethically approved non-medicinal item of equivalent weight, in order to maintain clinician concealment up to the point of randomisation; (ii) relevant items of trial paperwork (including the Symptom and Recovery Questionnaire and Trial Participation Card) and equipment (including a trial pen, a small gift appropriate for participating children, and a trial tote bag), and (iii) an appropriate number of pre-printed Participant ID number labels to affix to the trial paperwork for subject identification purposes. All OCS Patient Packs, also pre-labelled with the Participant ID number, will contain items (ii) and (iii) only. The Bristol trial centre will make up the patient packs (minus the medicine packs) and provide them to UH Bristol Pharmacy. UH Bristol Pharmacy will add to the Patient Packs a Medicine Pack in line with the randomisation schedule provided by BRTC. UH Bristol Pharmacy will keep a log of which Medicine Pack is allocated to which Patient Pack and will affix the appropriate Medicine ID and Participant ID numbers to the Trial Participation Card. Complete, sealed Patient Packs will be stored by UH Bristol Pharmacy and released by a pharmacist to the Bristol trial centre in batches for direct onward distribution to recruiting primary care sites.

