The Bristol trial centre will supply all participating primary care sites (including those led by Cardiff or Southampton) in small batches (of two RCT Patient Packs for the 2 arm pilot, increasing to batches of 3 once the placebo arm is introduced size to be confirmed), via same-day courier service in line with all applicable regulations. The Bristol trial centre will be the single point of contact for UH Bristol Pharmacy for the purposes of the trial. The Bristol trial centre will keep a log of which Patient Packs are sent to which recruiting primary care site, with all Patient Packs signed for on receipt at the GP practice and a faxed, completed requisition and transfer form will be sent to the Bristol trial Centre detailing the Participant ID numbers received at the site. Sites will liaise with their local Centre when more packs are required, and the local centre will then make a request for additional packs to the Bristol Centre, which will send a further batch directly to the recruiting primary care site.

From the point at which the placebo is available, participating sites will be transferred from the 2 arm pilot into the 3 arm trial once they have used up their allocation of 2 arm Patient Packs. Any new site joining the trial after the point of placebo availability will be set up to run the 3 arm trial.

Recruiting primary care sites will store the medicines in the manner approved by the MHRA and protect them from light and excessive humidity.

On completion of the baseline questionnaire (CRF) online the clinician will enter the Patient ID number.

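### Appendix 9 describes an allocation process that conflicts with sections 7.2, 9.6 and 12.3 and, if followed, would weaken concealment of drops versus no drops

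*Protocol*

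**What the plan says.** The body of the protocol describes one process. Under section 7.2 the central pharmacy completes each Patient Pack with either a Medicine Pack "or an ethically approved non-medicinal item of equivalent weight, in order to maintain clinician concealment up to the point of randomisation". On contents, "Each Medicine Pack will contain two bottles of either the active or the placebo solution". Sites receive complete sealed packs. Under section 9.6 the clinician takes the next number in sequence and opens the pack in front of the parent, and what is inside reveals drops or no drops. Section 12.3 agrees: packs look identical across the three arms, and clinicians are to have no means of influencing allocation.

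Appendix 9 describes another. Centres and sites receive sealed Patient Packs plus separate Medicine Packs, "each containing a bottle of the active or placebo ear drops". Of sites it says: "They will also be provided with a set of Medicine Packs which will be identified by the unique Medicine ID numbers", and "The sites will also receive Patient Packs and Medicine Packs in a proportion of 3:2". The Patient Pack holds only a Medicine ID number. For a child on drops, "the clinician will retrieve the single bottle of ear drops for which the Medicine ID number corresponds to that provided in the Patient Pack", and a colleague checks the match. Appendix 9 mentions no equal-weight item and no two-arm pilot.

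**The concern.** Both texts are in force, and Appendix 9 is the natural place for a site, pharmacist or monitor to look for the concealment rules. A site that followed it would have a shelf of Medicine Packs whose number shows how many drop allocations remain. Drops versus no drops is open once a pack is opened, so staff also know every earlier allocation at their site.

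This bears on the primary comparison, active drops against no drops. Entry rests partly on judgement: the clinician's diagnosis, the clinician's willingness to use a no-antibiotic or delayed strategy, and the parent's willingness to wait (section 6.2). The outcome is whether antibiotics are consumed. A recruiter who knew that no drops came next could, even unintentionally, hold back a child thought likely to need antibiotics. Selection of that kind cannot be undone in the analysis.

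**Working it through.** **1. The two processes side by side**

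| Item | Sections 7.2, 9.6, 12.3 | Appendix 9 |
|---|---|---|
| Where the medicine is held | Inside the sealed Patient Pack | Separate stock at centre and site |
| No-drops arm | Equal-weight item in the pack | No matching Medicine Pack |
| How allocation is learned | Opening the pack | Reading the Medicine ID in the pack |
| Bottles per Medicine Pack | Two | One |
| Two-arm pilot | Described | Absent |

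**2. The 3:2 figure**

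Section 12.3 uses blocks of 30 split 10:10:10, so 30 Patient Packs need 10 + 10 = 20 Medicine Packs, and 30:20 = 3:2. The figure reproduces. Appendix 9, however, explains it as the ratio of treatment arms to control, which is 20:10 = 2:1. In the two-arm pilot (10:10), Patient Packs to Medicine Packs would be 20:10 = 2:1, so 3:2 could not apply there.

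**3. Appendix 9 against itself**

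It later says the pharmacy keeps a log of which Medicine Pack went into which Patient Pack. That log makes sense only under the sealed-pack process.

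**4. What could be known in advance if Appendix 9 were followed**

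Suppose a supply holds d drop allocations and c no-drop allocations in random order, stock is visible, and it is used up before restocking. An allocation is certain in advance only when all remaining packs are of one kind, that is, within the final run of the sequence. The expected length of that run is

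d/(c + 1) + c/(d + 1).

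| Patient Packs | d, c | Expected number certain | Share |
|---|---|---|---|
| 3 | 2, 1 | 2/2 + 1/3 = 1.333 | 44% |
| 6 | 4, 2 | 4/3 + 2/5 = 1.733 | 29% |
| 9 | 6, 3 | 6/4 + 3/7 = 1.929 | 21% |
| 30 | 20, 10 | 20/11 + 10/21 = 2.294 | 8% |

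Direct check for 3 packs: the first is never known, the second is known if the first was no drops (1/3), and the third is always known. (0 + 1/3 + 1)/3 = 4/9 = 44%. Best-guess accuracy is (2/3 + 2/3 + 1)/3 = 77.8%, against a base rate of 66.7%.

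**5. The same question under sections 7.2 and 9.6**

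There is no Medicine Pack stock to count. Three consecutive packs from a 20:10 centre block contain exactly two drop packs with probability C(20,2) × C(10,1)/C(30,3) = 1,900/4,060 = 0.468, so earlier packs in the batch do not settle the last one. Best-guess accuracy stays at 66.7% and none is certain.

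**The case against.** The strongest reply is that the protocol makes clear which process operates. Sections 7.2, 9.6 and 12.3 agree with one another. Section 9.6 points to 7.2 and 12.3 for concealment, not to Appendix 9. The accountability table in section 7.5 has the pharmacy allocate Medicine Packs to Patient Packs and shows no separate medicine supply to sites. Appendix 1 lists those four sections, but not Appendix 9, as revised when medicine was moved inside the pack, which suggests how the mismatch arose. This stands: the defect is most likely an appendix that was not updated.

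Three stronger readings are tempting, and the documents do not support them.

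- A reader might infer that recruiters in this trial can predict the next allocation. A site supplied under 7.2 has no loose Medicine Packs to count.
- A reader might take 44% as the trial's figure. Loose packs come only from Appendix 9, which gives no supply size. The supply of three comes only from 7.2 ("increasing to batches of 3 once the placebo arm is introduced"), which adds that the size is to be confirmed. No stated process combines them, hence the range.
- A reader might infer that pilot batches of two and later batches of three hold one pack per arm, making the last allocation in each batch certain. The text does not say so. Section 12.3 sets blocks of 30 by centre (10:10 in the pilot), and consecutive packs from such a block are not balanced in small batches.

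What survives is that a current appendix states a rule that would defeat the concealment promised in 12.3.

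**Conclusion.** Appendix 9 is wrong as written. It contradicts sections 7.2, 9.6 and 12.3 on where the medicine is held, how allocation is revealed and how many bottles a pack contains. It also contradicts itself on the pack log and the meaning of 3:2, and leaves out the two-arm pilot.

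The threat to concealment is conditional on Appendix 9 being followed, on stock being visible, and on supplies running out before restocking. On those assumptions the share of allocations known for certain runs from 44% down to 8% as the supply grows from 3 to 30 Patient Packs. It concerns drops versus no drops only; the blinded active-placebo comparison of pain is not exposed. The sample size is unaffected. The point should be corrected because concealment cannot be restored after recruitment and the primary comparison depends on it.

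**What to change.** - Replace the distribution and matching paragraphs of Appendix 9 with the process in 7.2, 9.6 and 12.3: medicine or equal-weight item sealed in the Patient Pack by the pharmacy, no separate Medicine Pack stock at centres or sites, and no 3:2 supply rule.
- Add the two-arm pilot schedule to Appendix 9.
- Reconcile the number of bottles per Medicine Pack with section 7.2. The count also matters for drug accountability and for weighing returned bottles as the adherence measure (sections 7.6 and 7.10).
- State in 7.2 that site batches are consecutive numbers from the centre's randomisation block and are not balanced by arm within a batch. With that stated, no restriction on batch size is needed.

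The cost is a text replacement and one instruction to the pharmacy and trial centre, with no burden on families or sites.
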